**6.0 Study Visit Summaries:**

6.1 Screening Visit:

At this visit, the patient will be asked to provide written informed consent and inclusion and exclusion criteria will be evaluated to ensure that the patient meets all entrance criteria. See the Study Schedule of Activities section 7.17 for visit activities. After the informed consent process is complete, the subject will begin the run-in phase of the study.

Subjects may be enrolled if they are on a current Pentoxifylline regimen, but Investigators should not start patients on Pentoxifylline during the trial if the patient is not taking the drug at enrollment.

6.2 Run-in Visit:

There could be up to 4 visits during the run in phase, 3 visits if the Screening and Baseline visits occur on the same day. The visit schedule is as follows Screening/Baseline; Run-in Week 1 and Randomization ( $\pm 2$  days). The subjects will follow the treatment regimen outlined in section 7.17. At each visit the study staff will access the ulcer. If the subject meets any of the exclusion criteria listed in section 5.2.3 at the Randomization Visit the subject will be excluded from the study.

6.3 Randomization Visit:

At the randomization visit the subject will undergo procedures as outlined in the Study Schedule of Activities table in section 7.17.

The subject will leave the randomization visit with:

- Schedule for the next study visit (if possible, follow-up visits should be scheduled at the same time of day)
- Instructions on use and application of the assigned study apparatus, as applicable
- Diary and instructions to record daily activity
- Contact information and instructions to call if any problems arise

6.4 Treatment Visits (Weeks 1-16 or healed):

Investigational Group: Subjects will be seen in clinic at weeks 1, 2, 4, 6, 9, 12, 16 ( $\pm 2$  days) for 16 weeks or until the VLU is completely healed, as defined by complete closure with no open area or exudate. At the visits the subject will undergo the procedures as outlined in the Study Schedule of Activities table in section 7.17.

Control Group: Subjects will complete weekly visits for 16 weeks or until the VLU is completely healed, as defined by above. At the weekly visits the subject will undergo procedures as outlined in the Study Schedule of Activities table in section 7.17.

The study staff will review the subject diary with the subject during each visit to ensure that all entries are complete and understood by the study staff. Any corrections must be made by the subject, and initialed and dated by them.

6.5 Support Contact:

Subjects randomized to the ACTitouch arm of the study will be contacted by study personnel (via text or phone call). The first follow up contact will occur 3 days ( $\pm 1$  day) after the Randomization Visit and the second follow up contact will occur 3 days ( $\pm 1$  day) after the Treatment Week 1 Visit.

For the remainder of the VLU treatment period, follow up contact will occur on weeks that the subject is not returning to the clinic for a study visit. The subject will be contacted during treatment weeks 3, 5, 7, 8, 10, 11, 13, 14, and 15 ( $\pm 2$  days from optimal date). If an ACTitouch subject is seen for an unscheduled study visit

within one of these windows, this will take the place of the support contact for that week.

**6.6 Follow Up Visits (Months 1, 2 &3):**

Subjects who are assigned to the ACTitouch device and heal during the 16 week treatment period will continue to be seen monthly for 3 months ( $\pm 7$  days) post healed visit. At the visit the subject will undergo the procedures outline in the Study Schedule of Activities table in section 7.17.

The study staff will review the subject diary with the subject during each visit to ensure that all entries are complete and understood by the study staff. Any corrections must be made by the subject, and initialed and dated by them.

**6.7 Unscheduled Study Visit:**

The subject may return to the investigational site for unscheduled visits during the study. At this unscheduled study visit the subject will complete all study procedures as outlined in the Study Schedule of Events Section 7.17.

**6.8 Recurrence Visit:**

If the subject's VLU recurs during the 3 month follow up period the subject will be instructed to return to the investigational site to be assessed. At the visit the subject will undergo the procedures outlined in the Study Schedule of Activities table in section 7.17.

**7.0 Study Procedures:**

**7.1 Pre-screening:**

Pre-screening of potential subjects will be conducted by study staff either by phone or in person. Potential subjects who are interested in participating in the study will meet with study staff in-person for the consent process.

**7.2 Informed Consent:**

Informed consent must be obtained from all subjects prior to participation in clinical studies as mandated by Federal Regulations and/or the qualifying Institutional Review Board/Ethics Committee (IRB/EC). A blank copy of the IRB/EC-approved informed consent form must be kept on-site and by Tactile Medical. The signed original for each subject must be kept in the subject's medical records.

A copy of the consent will be given to the subject to read and take home to consider if they prefer. All questions must be answered prior to signing the informed consent form. Clinical study procedures cannot be performed until subject signs the consent. A signed copy of the consent should be provided to the subject.

**7.3 Laboratory Testing:**

After providing informed consent, women of child bearing potential will be tested for pregnancy at the site specific clinical laboratory according to site standard

procedures. If the pregnancy test is positive, subjects will be excluded from the study.

Subjects with diabetes must have a HbA1c value  $\leq$  12% within the past three (3) months. If the subject does not have a documented HbA1c at the time of consent then one must be completed after providing informed consent but before randomization. If the HbA1c is  $>$  12% the subject will be excluded from the study.

All potential subjects must have a dorsalis pedis (DP), posterior tibial (PT), TcP02, or great toe pressure as outlined in the criteria within the last six months to meet study eligibility, unless approval is obtained from the Sponsor Chief Medical Officer. If the aforementioned tests are  $>$  6 months or the subject hasn't undergone one of the required tests one will need to be completed to determine eligibility.

#### 7.4 Randomization:

After completing the informed consent process, subjects who meet the entrance criteria will complete the Run-in Phase before being randomly assigned into either the multi-layer bandage or ACTitouch group. The scheme will be generated randomly, electronically by Clindex, and will be stratified based on ulcer size and duration at time of randomization.

For the purpose of this study, multi-layer bandages include PROFORE and Coban 2 only. The use of multi-layer bandaging other than the pre-specified bandages will be considered a deviation from the protocol and must be reported to the sponsor immediately. This deviation could result in termination of the study subject.

#### 7.5 Leg Volume Measurements:

Circumferential measures of both legs will be taken at 4cm intervals starting at 10cm up from the bottom of the subject's heel, flexed at 90 degrees to the leg and continue to the knee at the popliteal fold (Appendix D). If possible, the same clinician will be asked to take the measurements for each patient visit.

#### 7.6 Wound Assessment:

At each study visit (if applicable) the ulcer will be assessed by qualified study personnel. The ulcer features that will be assessed will include ulcer drainage, type and amount, ulcer bed features, wound margin, and periwound areas; and other aspects including but not limited to odor, pain, and debridement.

Ulcer closure/healing is defined by 100% epithelialization and no drainage.

#### 7.7 Wound Debridement:

Ulcer debridement will be undertaken as needed per the investigator's clinical decision. The methods of debridement may include enzymatic, sharp, surgical, and mechanical debridement and/or pulse lavage.

7.8 Wound Dressings:  
All subjects will undergo wound dressing changes, either in the clinic or at home. Wound dressing will be selected by the investigator. Generally, “dry ulcers” will require hydrocolloid dressings and “wet ulcers” will require foam or alginate.

7.9 Wound Photograph and Tracing:  
At each study visit, (if applicable) the study ulcer will be photographed and the wound will be traced using the Silhouette™ system (Appendix E).

In addition, at the initial visits all ulcers on the study limb will be photographed and traced to ensure that the sum of the areas is not greater than 50cm^2. Any ulcers that form on the study limb during the course of the study will also be photographed and traced for AE documentation.

The initial visit, enrollment visit, and healed visit image and tracing will be evaluated by a single independent adjudicator to increase integrity and to provide a blinded analysis. Ulcer surface areas that fall on or near the minimum or maximum ulcer surface area allowed for study inclusion will be adjudicated in a timely manner. Study staff will have access to the adjudication results by a time no later than the next scheduled subject visit.

7.10 Tissue/Skin Assessment:  
The subject’s legs will be examined for irritation, trauma and ulceration at each study visit. At any time during the study the investigator may determine that a tissue/skin change requires the subject to be withdrawn from the study.

7.11 Compression Application:  
Application of ACTitouch System:  
The ACTitouch system will be applied by the trained study staff. First the ACTitouch under-sock will be applied. The sock will be in direct contact with the skin and wound dressings and the ACTitouch sleeve will wrap around the pre-covered leg. The ACTitouch will be applied while the subject is seated, with the feet lightly resting on the floor.

Application of Multi-Layer Bandaging:  
The trained study staff will apply the multi-layer bandaging according to manufacturer’s instructions. The multi-layer bandaging will be in direct contact with the skin and the wound dressings.

7.12 Application Timing:  
The time to apply compression by study personnel on the subject’s limb in clinic will be recorded throughout the study as specified (section 7.16). Both treatment application methods will be timed and recorded. The study personnel will lay out all required materials to be applied. Immediately after the timing starts either the first contact layer in the multi-layer bandaging group or the under-sock of the

- 7.13 Compliance Assessment:  
Subject compliance will be evaluated through the support call, subject diary, interview, and ACTitouch Compliance Tracker (for the subjects randomized to ACTitouch) at each study visit.
- 7.14 Cost: A sub-study evaluating economics will also be included in this study. The economic sub-protocol outlines the collection of essential health economic items concerning visits, procedures and lab tests, QOL and work productivity. (Appendix G).
- 7.15 Study Surveys/Questionnaires: Subjects and study clinicians will complete survey/questionnaires to assess symptoms, quality of life, acceptance/tolerability, and ease of use of their assigned device.

Charing Cross Venous Ulcer Questionnaire: Consists of 21 items for the assessment of patients' perception of their health when venous ulceration is present, to be used in conjunction with the SF-36. (Appendix H)

[figure not shown]
Venous Clinical Severity Score (VCSS): A disease severity measurement tool including clinical descriptors that have the ability to change over time which allows for improvements to be captured. (Appendix J)

## 7.16 Study Schedule of Activities

Run In / Treatment Periods:

Follow Up Period:

Key: *Active Ulcer	Follow Up Month 1	Follow Up Month 2	Follow Up Month 3	VLU recurrence visit

**8.0 Study Device Accountability:**

Site personnel must maintain device accountability log(s). Completion of these log(s) will ensure that all ACTitouch Control Units and Sleeves are properly tracked and accounted for throughout the study from the time they are received by the institution to the time they are returned to Tactile Medical. Device location, Subject ID assigned, date, and final disposition (e.g., returned to Tactile Medical, garments discarded, garments retained by subject) of all ACTitouch Control Units and Sleeves will be documented. Tactile Medical must also maintain device accountability documenting all shipments and returns of Control Units by serial number, date, and person completing the log. Storage locations for the Control Units and Sleeves will be secure (i.e., locked and away from other devices) with access restricted only to investigators and authorized research personnel.

Sanitation Procedure:

At the conclusion of the study, the subject must return the ACTitouch controller to the investigational site. The site personnel will disinfect the Control Unit by thoroughly cleaning it with a disinfectant before it can be reassigned to a subject or returned to the Tactile Medical. The subjects may keep the sleeve and under-socks. If sleeve and under-socks are returned to the site they **CANNOT** be reused on multiple subjects and should be appropriately discarded upon study return.

**9.0 Risk Analysis and Adverse Events:**

9.1 Risk Analysis:

The subjects enrolled in the study are not expected to be at any higher or additional risk than those who use non-study pneumatic compression devices. There is risk with using any IPC device. These may include, but are not limited to risk of explosion if the device is used in the presence of flammable gases, risk of electrical

shock if the device is immersed in water or if the housing is broken and subject attempts to service the unit.

IPC devices are contraindicated for use in the presence of pulmonary edema, acute thrombophlebitis, congestive heart failure, acute deep vein thrombosis, episodes of pulmonary embolisms, acute infection, and inflammation or other conditions where increased venous or lymphatic return is undesirable.

There are minimal side effects expected from either treatment subjects will receive in this study and the study uses only currently FDA cleared interventions. The expected risks are often a failure to respond to the treatment intervention and are not related to the treatment itself. In some cases, side effects due to CVI or VLUs can be serious, long lasting, or may be permanent. The risks listed below are symptoms of CVI and/or VLUs and may be experienced by all subjects:

- Pain or discomfort
- Swelling of the lower legs/ankles
- Aching or tiredness in the legs
- Leathery looking skin
- Flaking or itching of the skin
- Stasis ulcers

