	
participation.
 
Exclusion:
 
 
• Target ulcer or any other ulcer on the study limb involves exposure of tendon, muscle, or bone.
 
• Treatment of the target ulcer with living cellular therapy within 30 days of the time of projected randomization.
 
• Endovenous ablation or other venous surgery within two weeks of enrollment. 
 
○ Venous ultrasound must be completed after procedure to determine whether there is still venous insufficiency at the time of enrollment.
 
 
 
• Acute deep vein thrombosis (DVT) or pulmonary embolism (PE) within the last 3 months.
 
• Acute thrombophlebitis within the last 6 weeks.
 
• History of pulmonary edema or decompensated congestive heart failure within 6 weeks of screening.
 
• Currently has an active infection of the skin on target limb such as cellulitis requiring antibiotics.
 
• History of target limb cancer within the last 2 years with the exception of treated non-melanoma skin cancer unless ulcer biopsy performed at screening is negative for neoplasia.
 
• Active cancer receiving chemotherapy and/or radiation therapy.
 
• Poorly controlled diabetes with an HbA1c value of > 12% within the past 3 months.
 
• Changes to medications that affect edema within the last 30 days.
 
• Use of systemic corticosteroids requiring daily administration at doses greater than 5 mg of Prednisone per day or equivalent for greater than 2 weeks.
 
• Currently pregnant or trying to become pregnant.
 
• Inability or unwillingness to participate in all aspects of study protocol.
 
 
Exclusions after a 2 week run-in:
 
 
• If ulcer area has decreased by greater than 30% compared to baseline area, the subject will be removed from the study.
 
• Ulcers measuring less than 1.5cm^2 after the run in.
 
• Ulcers increasing in size greater than 50% after run.
 
• Any ulcer appearing to have evidence of infection.
 
• If the sum of the ulcer areas on the study limb is > 50cm^2 the subject is not eligible to participate in the study.
 

ASSESSMENTS	

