  - Endovenous ablation or other venous surgery within two weeks of enrollment
    - Venous ultrasound must be completed after procedure to determine whether there is still venous insufficiency at the time of enrollment.
  - History of skin sensitivity to any of the components of AT, multi-layer bandages or compression garments.
  - History of an acute deep vein thrombosis (DVT) or pulmonary embolism (PE) within the last three (3) months.
  - Acute thrombophlebitis within the last six (6) weeks.
  - History of pulmonary edema or decompensated congestive heart failure within six (6) weeks of screening.
  - Currently has an active infection of the skin on the target limb such as cellulitis requiring antibiotics.
  - History of target limb cancer within the last two years with the exception of treated non-melanoma skin cancer unless ulcer biopsy performed at screening is negative for neoplasia.
  - Active cancer receiving chemotherapy and/or radiation therapy.
  - Poorly controlled diabetes with an HbA1c value of > 12% within the past three (3) months.
  - Changes to medications that affect edema within the last 30 days prior to enrollment (e.g. diuretics, calcium channel blockers of the dihydropyridine class, pioglitazone, cox-1 inhibitors, pregabalin, and gabapentin, diltiazem or fluctuating doses of systemic steroids).
  - Use of systemic corticosteroids requiring daily administration at doses greater than 5mg of Prednisone per day or equivalent for greater than two weeks.
    - Low dose steroid administration (Prednisone up to 5mg per day or equivalent) is allowable for an unlimited period of time. Topical steroid administration to peri-ulcer area or other skin is allowable but cannot be applied to the ulcer itself.
  - Currently pregnant or trying to become pregnant.
  - Inability or unwillingness to participate in all aspects of study protocol.
  - Exhibit any condition which, according to the Investigator, justifies the subject's exclusion from the study, such as a medical condition where an increase in venous or lymphatic return is undesirable.
  - Currently participating in another clinical trial.

5.2.3 Additional Exclusions after two week run-in: Subjects will exit the study if they meet any of the following criteria:

- Subject's target ulcer has decreased in size by greater than 30% compared to the baseline area.
- Subject's target ulcer has increased in size by greater than 50% compared to the baseline area.

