- Subject's target ulcer measures less than 1.5cm^2 at the Randomization Visit.
- Subject appears to have evidence of infection in any ulcer.
- The sum of the ulcer areas on the subject's study limb is > 50cm^2.

5.2.4 Subject Withdrawal or Early Termination:

Subjects will exit the study if they meet any of the following criteria:

- Subject death
- Subject voluntarily withdraws or investigator's decision
- Subject experiences an adverse event that in the investigator's clinical judgment necessitates study discontinuation
- Ulcer recurrence during the 3 month follow up period
- Subject acquires any of the exclusion criteria, except
  - If subject acquires an infection, they may be treated for the infection and continue in the trial in the investigator's discretion. The investigator can instruct the subject to cease sustained or IPC treatment for up to two (2) consecutive weeks but no more than four (4) weeks total. If the subject is required to abstain from study treatment for greater than the amount described above, the subject will be removed from the study.

5.3 Dosage:

Run-in

All subjects will participate in a two week run-in phase. The treatment will include multi-layer compression bandaging which must be worn 24 hours a day except during clinic visits. The run-in phase is intended to assess the subject's initial response to standard of care treatment using multi-layer bandaging before receiving treatment with the investigational device.

VLU Treatment Period

All subjects enrolled will be randomized into either treatment using the ACTitouch system or multi-layer bandaging which consists of either PROFORE or Coban 2.

Investigational Group: Subjects assigned to the ACTitouch system must wear the device in sustained mode during all wakeful hours (at least 12 hours each day) and IPC mode for a minimum of 2 hours each day. Subjects will be instructed to remove the ACTitouch for bathing and when driving or operating machinery, and reapply immediately after these activities.

At each visit the subject’s compliance will be evaluated via the compliance tracker on the ACTitouch device.

Subjects randomized to the ACTitouch arm of the study will also be contacted weekly between study visits by study personnel to support device compliance and answer questions as outlined in Section 7.16.

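### The protocol calls IPC contraindicated in congestive heart failure and acute infection, but its heart failure exclusion is narrower and its treatment pause for infection is optional

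*Protocol*

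**What the plan says.** **Risk statement.** Protocol 9.1 (Risk Analysis) says "IPC devices are contraindicated for use in the presence of pulmonary edema, acute thrombophlebitis, congestive heart failure, acute deep vein thrombosis", and the list continues with "episodes of pulmonary embolisms, acute infection, and inflammation or other conditions where increased venous or lymphatic return is undesirable". Heart failure carries no qualifier for severity or stability and no time window. Infection is qualified only as acute.

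**Entry.** Protocol 5.2.2 (Exclusion Criteria) excludes "History of pulmonary edema or decompensated congestive heart failure within six (6) weeks of screening". The Synopsis has the same restriction: "History of pulmonary edema or decompensated congestive heart failure within 6 weeks of screening". A general criterion near the end of 5.2.2 lets the investigator exclude for any condition judged to justify it, "such as a medical condition where an increase in venous or lymphatic return is undesirable". Section 5.2.2 also excludes current active skin infection of the target limb, and 5.2.3 removes subjects with signs of infection in any ulcer after the run-in.

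**On study.** Under 5.2.4 a subject who acquires an exclusion criterion leaves the study, with infection as the one exception: "If subject acquires an infection, they may be treated for the infection and continue in the trial", at the investigator's discretion. On interruption, "The investigator can instruct the subject to cease sustained or IPC treatment for up to two (2) consecutive weeks", with a ceiling of four weeks in total. Removal is required only if a longer abstention is needed.

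**Exposure.** Section 5.3 (Dosage) has ACTitouch subjects use IPC mode for at least two hours a day, in addition to sustained mode. Those who heal continue the device for three more months.

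**The concern.** In the text available, 9.1 is the only place where the protocol names the conditions in which pneumatic compression should not be used. One would expect the eligibility, exit and pausing rules either to reproduce that list or to explain why they depart from it. On two items they do neither. A site could apply every listed criterion correctly and still have a subject on daily IPC in a state that the protocol itself calls contraindicated, while another site, guided by 9.1, would handle the same subject differently.

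What is at stake is first the safety of subjects on the device. These are also events that the trial means to count: 9.3 makes study-limb infection and new or worsened heart failure reportable adverse events, and 12.3.4 makes ulcer infection a safety endpoint.

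**Working it through.** No arithmetic applies; the check is a comparison of the passages.

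| Condition | Protocol 9.1 | Entry and run-in (5.2.2, 5.2.3, Synopsis) | On study (5.2.4) |
|---|---|---|---|
| Heart failure | Contraindicated, unqualified | Excluded only if decompensated and within six weeks of screening; otherwise investigator's judgment | Exit if an exclusion criterion is acquired |
| Acute infection | Contraindicated | Active target-limb skin infection excluded; infected ulcer after run-in leads to exit | Exempt from exit; pause allowed but not required |

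**Heart failure.**
1. The condition in 9.1 is any congestive heart failure. The named criterion is a subset of it, limited by both state and time.
2. A subject with known stable heart failure, or whose last decompensation was seven weeks before screening, falls inside 9.1 and outside the named criterion.
3. The other venous and cardiopulmonary items in 9.1 (pulmonary edema, acute thrombophlebitis, acute deep vein thrombosis, pulmonary embolism) each reappear in 5.2.2 with a look-back window that covers the current condition. Heart failure alone gains a narrowing qualifier that 9.1 lacks.
4. The general criterion in 5.2.2 echoes the closing words of 9.1, but it does not name heart failure and depends on the investigator's view.
5. Section 9.3 lists heart failure that worsens separately from heart failure that first appears. This implies that some subjects were expected to have heart failure at entry.

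**Infection.**
1. Up to randomization, the rules point the same way as 9.1.
2. After randomization, 5.2.4 removes the automatic exit. It keeps the subject in the trial, which is not the same as keeping the subject on the device.
3. The verb governing the pause is *can*. The only mandatory step is removal once the two-week or four-week limit would be exceeded.
4. If the investigator pauses the device, 5.2.4 and 9.1 are both satisfied. If the investigator does not, 5.2.4 is still satisfied and 9.1 is not. The defect is confined to that second case.

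**Which arm.** The pause sentence speaks of sustained or IPC treatment. These are the ACTitouch modes in 5.3, but the device descriptions also call the PROFORE bandage's compression sustained, and the next sentence of 5.2.4 refers to study treatment without naming an arm. The text does not settle whether the pause rule covers bandage subjects.

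**The case against.** The strongest reply is that 9.1 is a description of risk for a class of devices, not an instruction to sites. The operative rules are in 5.2.2 to 5.2.4; they carry over most of the 9.1 list, and the general criterion gives the investigator a route to exclude the rest. Other safeguards exist: subjects who acquire any other exclusion criterion exit, the investigator may discontinue a subject for an adverse event, and the DSMB expects to review safety data quarterly. The device description is incomplete in the available text and the appendices are not included, so device-specific instructions may exist there.

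Much of this stands as mitigation. It does not remove the heart failure mismatch, because a discretionary criterion does not exclude what 9.1 states without condition, and the protocol gives no reason for the narrower rule. Any unseen material would still have to be reconciled with the sections quoted here.

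On infection the objection carries more weight. A reader might infer that the protocol directs IPC during acute infection, or that every infection in the ACTitouch arm falls under two conflicting rules. The documents do not support either reading: 5.2.4 speaks of staying in the trial, provides for interruption, and is compatible with 9.1 whenever the device is paused. A reader might also infer that bandage subjects have no rule at all; the wording is ambiguous on that, not silent.

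**Conclusion.** The point holds as an internal contradiction on heart failure and as an over-permissive rule on infection. On heart failure, the contraindication is broader than the exclusion, and only investigator judgment covers the difference. On infection, the fault is narrower: nothing requires the device to be stopped during an acute infection acquired on study.

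The size cannot be given. The documents state neither how many subjects will have heart failure at entry nor how many will acquire an infection, and the contradiction does not depend on either figure. A reader might infer that the comparison of safety between arms is distorted. That could follow if sites handled such subjects differently, but the documents do not show it. Nothing here touches alpha, the non-inferiority margin or the sample size.

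The conclusion rests on reading 9.1 as the protocol's own statement about the investigational modality, and on the text available. It should be fixed because it is wrong as written, bears on patient safety and is cheap to correct; it does not call the design into question.

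**What to change.** Amend the protocol under 11.6 so that:

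- 9.1, 5.2.2 and the Synopsis carry one statement on heart failure, which also governs continuation on study;
- 9.1 and 5.2.4 carry one statement on acute infection, which makes clear whether interruption of the device is required or optional and keeps the entry and post-run-in rules consistent with it;
- the same place states whether the pause rule applies to both arms.

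Which clinical rule to adopt is for the sponsor's medical lead and the DSMB; this review takes no position on it.

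The cost is amendment wording, IRB approval and a letter to sites. Depending on which text is kept, either the risk section or the eligibility and pause text changes. If the eligibility text is the one that changes, there may be somewhat fewer eligible subjects.
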